12.3. ADVERSE EVENTS AND SERIOUS ADVERSE EVENTS

12.3.1. DEFINITION OF ADVERSE EVENTS (AE)

An adverse event (AE) is defined as any untoward or unfavorable medical occurrence in a human patient or research subject, including any abnormal sign (for example, abnormal physical assessment or laboratory finding), symptom, or disease, temporally associated with the subject's participation in the research, whether or not considered related to the subject's participation in the research. Adverse events occurring after the participant provides informed consent will be recorded.

12.3.2. DEFINITION OF SERIOUS ADVERSE EVENTS (SAE)

An adverse event (AE) or suspected adverse reaction is considered "serious" if, in the view of either the investigator or sponsor, it results in any of the following outcomes:

- death
- a life-threatening adverse event
- inpatient hospitalization ≥ 24 hours or prolongation of existing hospitalization
- a persistent or significant incapacity or substantial disruption of the ability to conduct normal life functions, or
- a congenital anomaly/birth defect
- Is an important medical event that may not be immediately life-threatening or result in death or hospitalization but may jeopardize the participant and may require intervention to prevent one of the other outcomes listed in the definition above.

This definition permits either the sponsor or the investigator to decide whether an event is serious. Serious adverse events are critically important for the identification of significant safety problems. Therefore, if either the investigator believes that the event is serious, the event must be considered serious and evaluated by the sponsor for expedited reporting (21 CFR 312.32(a) and 312.32(c)(1)).

12.3.3.CLASSIFICATION OF AN ADVERSE EVENT

Severity of Event

For adverse events (AEs), the following guidelines will be used to describe severity.

- **Mild** Events require minimal or no treatment and do not interfere with the participant's daily activities.
- **Moderate** Events result in a low level of inconvenience or concern with the therapeutic measures. Moderate events may cause some interference with functioning.
- **Severe** Events interrupt a participant's usual daily activity and may require systemic drug therapy or other treatment. Severe events are usually potentially life-threatening or incapacitating. Of note, the term "severe" does not necessarily equate to "serious".

Relationship to study intervention

The site investigator is responsible for assessing the relationship between the AE and the study agent(s). Site investigators must provide the initial assessment as to whether there is a reasonable possibility that the study agent(s) caused or contributed to a SAE. The relationship assessment, based on clinical judgment, often relies on the following:

- A temporal relationship between the event and administration of the study agent(s),
- A plausible biological mechanism for the agent to cause the AE,

- Another possible etiology for the AE,
- Previous reports of similar AEs associated with the study agent or other agents in the same class, and
- Recurrence of the AE after re-challenge or resolution after de-challenge, if applicable.

Further assessment of causality is provided by the DSMB based on accumulating safety reports between treatment groups.

The terms used to assess the relationship of an event to study agent are:

- Related There is a reasonable possibility that the AE may be related to the study agent(s).
- Not Related There is not a reasonable possibility that the AE is related to the study agent(s).

Expectedness

Expected AEs are AEs that have been previously observed with the study intervention or procedures. An adverse event is considered "unexpected" if its nature, severity, or frequency is **not** consistent with either of the following:

- the known or foreseeable risk of adverse events associated with the procedures involved in the research that are described in (a) the protocol-related documents, such as the IRB-approved research protocol, any applicable investigator brochure, and the current IRB-approved informed consent document, and (b) other relevant sources of information, such as product labeling and package inserts; or
- the expected natural progression of any underlying disease, disorder, or condition of the subject(s) experiencing the adverse event and the subject's predisposing risk factor profile for the adverse event.

12.3.4.TIME PERIOD AND FREQUENCY FOR EVENT ASSESSMENT AND FOLLOW-UP

The occurrence of an adverse event (AE) or serious adverse event (SAE) may come to the attention of study personnel during study visits and interviews of a study participant presenting for medical care, or upon review by a study monitor.

All AEs including local and systemic reactions not meeting the criteria for SAEs will be captured on the appropriate case report form (CRF). Information to be collected includes event description, time of onset, clinician's assessment of severity, relationship to study intervention (assessed only by those with the training and authority to make a diagnosis), and time of resolution/stabilization of the event. All AEs must be documented appropriately regardless of relationship. All AEs will be followed to adequate resolution.

Any medical condition that is present at the time that the participant is screened will be considered as baseline and not reported as an AE. However, if the study participant's condition deteriorates at any time during the study, it will be recorded as an AE.

Changes in the severity of an AE will be documented to allow an assessment of the duration of the event at each level of severity to be performed. AEs characterized as intermittent require documentation of onset and duration of each episode.

A site physician investigator or sub-investigator will record all reportable events between the time the participant provides informed consent through 4 weeks after their last treatment. At each study visit,

the investigator will inquire about the occurrence of AE/SAEs since the last visit. Events will be followed for outcome information until resolution, stabilization, or participant is off-study.

12.3.5.ADVERSE EVENT REPORTING

Serious Adverse Event Reporting

Study investigators will immediately notify the DAC of any serious adverse event, whether or not considered test treatment-related, including those listed in the protocol or investigator brochure. The report must include an assessment of whether there is a reasonable possibility that the treatment caused the event.

All serious adverse events (SAEs) will be followed until satisfactory resolution or until the site investigator deems the event to be chronic or the participant is stable. Other supporting documentation of the event may be requested by the DAC and should be provided as soon as possible.

- All AEs will be reported in aggregate to the NIAMS and the DSMB (through the NIAMS Executive Secretary) as part of the routine DSM report.
- All SAEs (regardless of relatedness or expectedness) will be reported to the NIAMS and the DSMB (through the NIAMS Executive Secretary) within 48 hours of the investigator becoming aware of the event.

12.3.6. REPORTING EVENTS TO PARTICIPANTS

Participants will be informed of any adverse events or serious adverse events if risk-benefit profile is impacted. Events significantly impacting the study integrity will require a change in protocol and additionally require re-consenting of participants. All active study participants would then be notified.

An abnormal finding may occur whenever imaging, conducting assessments, performing interventions, or completing study tasks. The purpose of imaging, assessments, and interventions are for research purposes only and are not intended to be used for clinical care (i.e., images will not be read by a radiologist). The imaging will not be read for clinical purposes and will not be reported to the patient (e.g., findings of spinal stenosis, neuroforaminal stenosis, lipomatosis, arachnoiditis will not be reported to the patient as the purpose is not for clinical care). During the course of the study, any gross abnormal finding noted in imaging or other assessment may be disclosed to the participant by the site investigator and the patient would be asked to follow-up with their Primary Care Physician (PCP). If the patient does not have a primary care provider, they will be instructed to establish care with a PCP to discuss further clinical management of the abnormal finding. Site investigators will work with DAC staff to notify participants and ensure that the patients are informed to follow-up with their PCP.

Examples of findings of clear clinical significance include:

- Abnormal blood pressure
- Intracranial abnormalities (e.g., hematoma, tumor)
- Intraspinal abnormalities (e.g., intraspinal tumors)
- Syncope during blood draws
- Pathological reflexes

Any other condition/finding in the discretion of the investigator that needs to be reported to the patient and assessed by a clinician/PCP.

12.4. UNANTICIPATED PROBLEMS

12.4.1.DEFINITION OF UNANTICIPATED PROBLEMS (UP)

Unanticipated Problem Involving Risk to Participants or Others (UPIRSO): Any incident, experience, or outcome that:

Is unexpected (in terms of nature, severity, or frequency) given (a) the research procedures that are described in the protocol-related documents, such as the IRB-approved research protocol and informed consent document; and (b) the characteristics of the participant population being studied; Is related or possibly related to a participant's participation in the research; and Is serious or suggests that the research places participants or others at a greater risk of harm (including physical, psychological, economic, or social harm) than was previously known or recognized.

12.4.2. UNANTICIPATED PROBLEM REPORTING

The investigator will report unanticipated problems (UPs) to the reviewing IRB, as required, and to the DAC. The UP will be entered into the DMS and will include the following information:

A detailed description of the event, incident, experience, or outcome;

An explanation of the basis for determining that the event, incident, experience, or outcome represents an UP;

A description of any changes to the protocol or other corrective actions that have been taken or are proposed in response to the UP.

All UPs will be reported to the NIAMS and the DSMB (through the NIAMS Executive Secretary) within 48 hours of the investigator becoming aware of the event.

13. STATISTICAL CONSIDERATIONS

13.1. STATISTICAL HYPOTHESES

The general objective of this study is to inform a precision medicine approach to cLBP. The statistical focus is on the estimation of a dynamic treatment regime (DTR) rather than to test the overall effectiveness of any single intervention or combination of interventions. The DTR will be estimated after the trial is completed, and it will use a panel of features, i.e. phenotypic markers, collected at baseline to recommend a first-line treatment, and then, depending on the response to treatment and any changes in participant covariates, recommend a second treatment (which may be a continuation of the first-line treatment). The performance will be measured by the estimated mean improvement in a given outcome (i.e. the PEG for the primary analysis) after two stages of treatment relative to baseline if the DTR were used to select treatments (called the value of the DTR). It is important to note that this goal

encapsulates discovering phenotypic markers that are associated with improved treatment response because the outcome is a function of the treatment received and a participant's covariates.

This section is intended to give an overview of the estimation targets for each study objective for the primary efficacy endpoint: the 24-week change from baseline in the PEG composite score. The PEG is a three-item scale with each item rated on a 0-10 scale. The mean response on these items will be used as the outcome.

The primary objective is to estimate an algorithm to assign sequences of two cLBP treatments based on phenotypic markers and an individual patient's response to the initial treatment (*i.e.*, a dynamic treatment regime) that optimizes effectiveness.

The goal is to estimate a DTR that maximizes the expected improvement in PEG after two stages of treatment relative to baseline. The estimation targets for this goal are 1) the parameters of the DTR and 2) the value of the estimated DTR.

To specify this formally, we will introduce notation from precision medicine (for a detailed review of this literature see Kosorok & Laber 2019). Let X_1 denote the participant's covariates at the time of the first randomization, and X_2 denote the interim data collected before the second randomization. A_t denotes the assigned treatment at the t-th stage randomization, and Y_t the difference between the PEG measured after completing the t-th stage course of treatment and the participant's baseline PEG score coded so that higher is better. Define H_t as the participant history available at the t-th stage randomization, so that $H_1 = (X_1)$ and $H_2 = (X_1, A_1, Y_1, X_2)$, and $H = (H_1, H_2)$. A dynamic treatment regime (DTR) is a sequence of functions $\mathbf{d} = (d_1, d_2)$ that maps participants to treatments based on the available history. An optimal DTR maximizes the expectation of a prespecified cumulative outcome $Y = f(Y_1, Y_2)$. In our case the outcome of interest is the 24-week change from baseline in PEG so $Y = Y_2$. The potential outcome under a regime \mathbf{d} is given by

$$Y^*(\mathbf{d}) = \sum_{(a_1, a_2)} Y^*(a_1, a_2) \mathbf{1}(d_1(H_1) = a_1) \mathbf{1}(d_2(H_2) = a_2)$$

where $\mathbf{1}$ is the indicator function that is equal to one when the condition is met and zero otherwise. The goal is to estimate $\mathbf{d}^{\mathrm{opt}}$, the DTR that maximizes the value function $V(\mathbf{d}) = E[Y^*(\mathbf{d})]$. The efficacy will be assessed in terms of the estimated value of the DTR $\hat{V}(\hat{\mathbf{d}})$. The optimal DTR, $\mathbf{d}^{\mathrm{opt}}$, is fundamentally unknowable in the same way that regression parameters are.

Secondary objective 1: Estimate DTRs that optimally balance multiple outcomes, taking into account participant preferences for outcomes including pain intensity, pain interference, physical function, opioid use, depression, anxiety, sleep duration and sleep disturbance.

A utility-based combination of multiple outcomes will be used Aim 2. These outcomes include level of pain, physical abilities, fatigue, anxiety, depressive symptoms, cognitive function, and overall enjoyment of life. Three combinations will be considered: 1) a combination of pain and physical abilities; 2) a combination of pain, physical abilities, and cognitive function; 3) a combination of all seven outcomes. By eliciting participant preferences between different outcomes, we can construct an optimal DTR that balances multiple competing outcomes and respects the relative importance of these outcomes to each participant (Butler et al). Future treatment decisions could be informed by administering the preference

elicitation tool in combination with the estimated DTR to guide treatment decisions. Participant preferences will be elicited at baseline through a series of discrete choice tasks, and participant satisfaction with treatment will be measured after each stage of treatment to help calibrate the preference estimation. The efficacy will be assessed in terms of the estimated value, or expected patient-tailored combination of outcomes, of the DTR. $\hat{V}(\hat{\mathbf{d}})$.

Secondary objective 2: Estimate DTRs that incorporate additional phenotypic markers (i.e., deep phenotyping) collected on a sub-set of participants.

Secondary objective 3: Assess whether effectiveness is sustained based on outcomes collected 24 weeks after randomization to the second treatment.

The change in the PEG composite score collected 24 weeks after the start of the second treatment relative to baseline will the efficacy endpoint for Secondary objective 3. This is identical to the primary efficacy endpoint except with a longer follow-up time. The efficacy will be assessed in terms of the estimated value of the DTR $\hat{V}(\hat{\mathbf{d}})$.

Exploratory objectives: Evaluate the (1) comparative effectiveness of individual treatments; (2) comparative effectiveness of different treatment regimes (i.e., a particular regime with a given set of rules at each decision point); and (3) impact of treatment order on outcomes.

We can test the null hypothesis that the value of two different DTRs are equal. Let \mathbf{d}^0 denote the best DTR that does not consider a participant's phenotype (the best zero-order DTR). This DTR assigns every participant the treatment with the best population average treatment effect. Let \mathbf{d}^{opt} denote the optimal DTR that considers participant phenotype. We can conduct two-sided tests of superiority of the hypothesis

$$H_0$$
: $\mathbf{V}(\mathbf{d}^0) = \mathbf{V}(\mathbf{d}^{\text{opt}})$
 H_1 : $\mathbf{V}(\mathbf{d}^0) \neq \mathbf{V}(\mathbf{d}^{\text{opt}})$

For the other interventions that are not the best, we can analogously define a DTR that always recommends each of these treatments and compare them to each other and to the optimal DTR.

13.2. SAMPLE SIZE DETERMINATION

Simulation Methodology Overview

Simulation studies were used to determine the sample size for the trial using a grid search over potentially feasible sample sizes. The outcome measure was the difference in PEG at 24 weeks relative to baseline. The performance metric of interest in the simulation studies was how close the value of the estimated dynamic treatment regime, $V(\widehat{\mathbf{d}_n})$, was to the value of the optimal dynamic treatment regime $V(\mathbf{d}^{\text{opt}})$ for the difference. The percentage of optimal value is equal to $V(\widehat{\mathbf{d}_n})/V(\mathbf{d}^{\text{opt}})$ (assuming $V(\widehat{\mathbf{d}_n})$ is non-negative and $V(\mathbf{d}^{\text{opt}})$ is strictly positive). Note that this is not a hypothesis test but a performance criterion that evaluates how close the estimated treatment regime is to the optimal treatment regime

The estimated value of the estimated dynamic treatment regime for each replicate was obtained using Monte-Carlo methods and an independent out-of-sample data set. First, an out-of-sample data set was

generated using the same data generating distribution as the one used to generate the trial data for a given simulation scenario. A dynamic treatment regime is estimated on the replicate study data using Q-learning. Then for every dynamic treatment regime, the estimated DTR is used to assign the out-of-sample participants to treatment sequences, and the estimated value of the DTR calculated (the expected outcome under each treatment is known for all out-of-sample participants). Finally, the ratio of the value from estimated DTR to the optimal DTR is calculated.

The analog to power in this setting is the probability that the ratio of the value from a DTR estimated on a trial with sample size n relative to the value of the optimal DTR is greater than or equal to a fixed performance cutoff δ .

$$P(V(\widehat{d_n}) \div V(d^{\text{opt}}) \ge \delta)$$

We chose a performance cut-off δ of 0.9, so that for a simulated trial to be considered a success the value of the DTR estimated on that simulation replicate's data must be within 90% of the optimal DTR's value.

There is no analog to Type-I error for this because a null scenario would imply that all treatments are equally ineffective and no biomarkers matter, and in this situation any dynamic treatment regime is trivially optimal.

Simulations were conducted using R version 4.0.4

Simulation Data Generation

The outcome after each stage, Y_t the outcome is defined as the difference in PEG between the follow-up visit at the end of the stage and the baseline PEG. The simulation outcomes are on the standardized effect size scale instead of the 0-10 scale. The outcome of interest, Y, is the difference in PEG at 24 weeks relative to baseline $Y = Y_2$.

Let $A_{t,k}$ denote the indicator function ${\bf 1}$ (Intervention k given for stage t) that is one whenever intervention k is given for stage t and zero otherwise. For the outcome after each stage, Y_t , denote the conditional expectation of Y_t given the history and intervention by $Q_t(H_t,A_t)=E[Y_t|H_t,A_t]$. Then the data generating model for one of the simulation scenarios with a single covariate associated with the outcome is:

$$\begin{split} Q_1(H_1,A_1) &= .1A_{1,0} + .25A_{1,1} + .3A_{1,2} + .4A_{1,3} + .3X_1A_{1,3} + .25X_2 - .25X_3 \\ Q_2(H_2,A_2) &= .1A_{2,0} + .25A_{2,1} + .3A_{2,2} + .4A_{2,3} + .3X_1A_{2,3} - .1A_{2,1}A_{2,2} - 1A_{2,1}A_{2,3} \\ &- .1A_{2,2}A_{2,3} + .25X_2 - .25X_3 \\ Y_1 &= Q_1(H_1,A_1) + \epsilon_1, \quad \epsilon_1 \sim N(0,1) \\ Y_2 &= Q_2(H_2,A_2) + \epsilon_2, \quad \epsilon_2 \sim N(0,1) \\ Y &= Y_2 \end{split}$$

Recall that in the first stage exactly one intervention can be given, while in the second stage one or two interventions may be given.

The covariates were generated independently with $X_1 \sim \text{Bern}(.5)$, $X_l \sim \text{Bern}(p_l)$, l=2,...,5 where and p_l ranges from 0.5 to 0.9 and X_l are coded to take values $\{-1,1\}$ instead of $\{0,1\}$ and an additional five normally distributed covariates N(0,.5). There were a total of ten covariates, one of which was

associated with the outcome through a treatment interaction, and two prognostic covariates that influence the outcome but was not associated with response to treatment. The $\,Q$ -functions were estimated using mis-specified models that included interaction terms for every treatment by covariate pair, and the models were fit by the Lasso.

These settings give rise to the following optimal rule:

X_1	A_1^{opt}	$A_2^{ m opt}$	Response to treatment at 24 weeks compared to baseline
$X_1 = -1$	Any intervention	$A_{2,1}$ and $A_{2,2}$ in combination	0.45
$X_1 = 1$	Any intervention	$A_{2,2}$ and $A_{2,3}$ in combination	0.9

The optimal rule above, \mathbf{d}^{opt} , has an average (over the values of X_1) response of (0.45+0.9) = 0.675. An example DTR with a value that is within 90% of the optimal value is:

X_1	$A_1^{ m opt}$	$A_2^{ m opt}$	Response to treatment at 24 weeks compared to baseline
$X_1 = -1$	Any intervention	$A_{2,1}$ and $A_{2,2}$ in combination	0.45
$X_1 = 1$	Any intervention	$A_{2,1}$ and $A_{2,3}$ in combination	0.85

Which assigns $A_{2,1}$ instead of $A_{2,2}$ as part of the combination for biomarker positive patients in stage two. The average response (over the values of biomarker X_1) is 0.65.

The table below shows \mathbf{d}^{opt} and other treatment rules for comparison.

Treatment Regime	Average response to treatment at 24 weeks compared to baseline
d ^{opt} (incorporates phenotypic markers)	0.675
Assign A_0 in both stages	0.1
Assign A_1 in both stages	0.25
Assign A_2 in both stages	0.3
Assign A_3 in both stages	0.4
Assign A_3 in the first stage and $A_{2,2}$ and $A_{2,3}$ in combination in the second stage (no phenotypic markers)	0.6

The probability of attaining a value within at least 90% of the optimal value for this scenario is 81% based on 5,000 replicates (Monte Carlo standard error ≈ 0.009)

The treatment effect sizes were based on systematic review by the Agency for Healthcare Research and Quality^{18,59} and an internal review conducted by the experts on BACPAC's Interventions Working Group. The standardized treatment effect sizes were assumed to be 0.25 for ACT, 0.3 for Duloxetine, and 0.4 for EEMT. The effect size for enhanced standard of care was assumed to be 0.1. Subgroup-specific effects were constrained so that the population average treatment effect was equal to the effect sizes from the systematic review.

Simulation Results

A total of 630 complete cases yields 80% probability to attain a value within at least 90% of the optimal value. Assuming $^{\sim}15\%$ of participants fail to complete the study through the primary efficacy endpoint, a total sample size of approximately 740 randomized would be sufficient to achieve at least 90% of the possible reduction in PEG 80% of the time. The 15% drop-out is intended as an upper-bound, not the actual anticipated drop-out, and is based on a threshold provided by experts in this area where they would have serious concerns about any study having above this rate of drop-out.

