10.4.4. MEASURES TO MINIMIZE BIAS: RANDOMIZATION AND BLINDING

The **first-stage randomization** will use a randomized version⁶¹ of the Minimization method^{62,63} to maintain marginal covariate balance. Minimization is an alternative to stratified permuted block randomization for maintaining (marginal) covariate balance across treatments that is better equipped to handle a larger number of factors to balance on. When a participant is randomized, a measure of the marginal discrepancy between treatments is calculated and the patient is randomized using a biased coin method where whichever treatment would make the discrepancy smallest has a higher probability and the other treatments have equal, smaller probabilities. Covariates included in minimization algorithm:

[figure not shown]
- Willingness to participate in deep phenotyping (yes/no)
- Depressive or anxiety symptoms (yes/no)
- Duration of pain symptoms (<5 years/≥5 years)
- Current use of opioid treatment (yes/no)

A total of approximately 740 participants will be randomized to ACT (n=185), duloxetine (n=185), ESC (n=185), and EBEM (n=185) and which will require recruitment of approximately 820 participants, anticipating that 10% will not be randomized due to failure to meet eligibility criteria at the end of the run-in phase and an estimated 15% will be lost to follow-up over the course of the study. Participants who did not complete required run-in procedures will not be randomized. In order to assign equal numbers of participants to each of the 4 study interventions, randomization probabilities will account

for the fact that certain participants, e.g., because of a contraindication, may be eligible for only 3 of the 4 treatments.

Second-stage randomization will occur at the end of the first treatment period. Response to treatment will be assessed using the PEG and PGIC. Based on these scores, individuals will be grouped into 4 response classes.

- Group 1 participants (PGIC 1-2 and PEG <4) are assigned to maintain the first-line treatment.
- Group 2 participants (PGIC 1-2, PEG ≥4) are assigned to maintain the current treatment and augment with a randomly selected additional treatment.
- Group 3 participants (PGIC 3-4) are randomized to an **augmentation treatment or to switch** to a new treatment.
- Group 4 participants (PGIC 5-7) are randomly assigned to switch to a second-line treatment.

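### The only printed sizing scenario (81%, optimum 0.675) assumes a Stage 2 regime that Section 10.4.4 does not allow, and its Monte Carlo standard error does not fit 5,000 replicates

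*Protocol*

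**What the plan says.** Protocol Section 13.2 sizes the trial by simulation. A simulated trial succeeds if the estimated regime reaches at least 90% of the value of the optimal regime. The section prints one data-generating model, described as "one of the simulation scenarios with a single covariate associated with the outcome". The only limit it places on Stage 2 is that "in the second stage one or two interventions may be given". Its optimal rule allows any of the four treatments in Stage 1. In Stage 2 it gives ACT plus duloxetine when X1 = -1 (0.45) and duloxetine plus EBEM when X1 = 1 (0.90), averaging 0.675. The result is stated as "The probability of attaining a value within at least 90% of the optimal value for this scenario is 81% based on 5,000 replicates", with a Monte Carlo standard error of about 0.009; no trial size is given. The results paragraph then says "A total of 630 complete cases yields 80% probability to attain a value within at least 90% of the optimal value", without naming a scenario, and that about 740 randomized "would be sufficient to achieve at least 90% of the possible reduction in PEG 80% of the time". Sections 4.1 and 7.1 repeat the 80%.

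Section 10.4.4 sets the Stage 2 options by response class:

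- "Group 1 participants (PGIC 1-2 and PEG <4) are assigned to maintain the first-line treatment".
- Group 2 augments.
- Group 3 is randomized to augment or switch.
- Group 4 switches.
- ESC starters with PGIC 3-7 augment instead of switching.
- Anyone who must stop Stage 1 treatment early is switched.

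Every augmentation in Table 10.1 is the Stage 1 treatment plus one other. The same section says that the sizing used assumed group proportions, but neither document prints them. The SAP's sample size section refers back to the protocol.

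**The concern.** The 80% is the only power-type statement for the primary objective, and its meaning depends on what counts as the optimal regime. The one optimum shown has no response classes, and its Stage 2 pair does not depend on the Stage 1 treatment. It therefore gives combinations to people whom this trial will only maintain or switch, and it treats all four Stage 1 starts as equally good.

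If the sizing runs did model the classes, the printed example misdescribes them. If they did not, the 80% refers to a different design. In either case a reader cannot tell what 90% of the optimum is worth for a regime the trial can deliver. The standard error beside the 81% also looks too large for 5,000 replicates.

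**Working it through.** **Inputs (Section 13.2).** Stage 2 main effects: ESC 0.10, ACT 0.25, duloxetine 0.30, EBEM 0.40 + 0.30·X1, with X1 = ±1 equally likely. Each pair among ACT, duloxetine and EBEM carries a penalty of 0.1. The ACT-EBEM coefficient is read as 0.1 because the section's own 0.85 for that pair requires it. The cut-off is 0.9.

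**1. Reproduce the printed optimum.**
- X1 = 1: duloxetine + EBEM = 0.30 + 0.70 - 0.10 = 0.90.
- X1 = -1: ACT + duloxetine = 0.25 + 0.30 - 0.10 = 0.45.
- Mean (0.90 + 0.45)/2 = 0.675. The 90% bar is 0.9 × 0.675 = 0.6075.

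**2. Apply Table 10.1 only, before response classes.** Best Stage 2 option by start:

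| Stage 1 | X1 = 1 | X1 = -1 | Mean |
|---|---|---|---|
| ESC | 0.80 | 0.40 | 0.60 |
| ACT | 0.85 | 0.45 | 0.65 |
| Duloxetine | 0.90 | 0.45 | 0.675 |
| EBEM | 0.90 | 0.30 | 0.60 |

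The value 0.675 is still reachable, but not from any start. Starting everyone on ESC or on EBEM falls below 0.6075.

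**3. Add the response classes.** The class shares are my assumption, taken as equal across Stage 1 treatments and X1. Let a share s fall in each of Groups 1 and 4.
- X1 = 1, EBEM start: 0.90(1 - 2s) + 0.70s (maintain EBEM) + 0.30s (switch to duloxetine) = 0.90 - 0.80s. A duloxetine start gives the same.
- X1 = -1, ACT start: 0.45(1 - 2s) + 0.25s + 0.30s = 0.45 - 0.35s. A duloxetine start gives the same.
- Mean: 0.675 - 0.575s.

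| s in each group | Best deliverable value |
|---|---|
| 5% | 0.646 |
| 10% | 0.6175 |
| 15% | 0.589 |
| 20% | 0.560 |

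The total share g of Groups 1 and 4 together at which the best deliverable value equals 0.6075:
- Even split: 2 × 0.0675/0.575 = 23.5%.
- 3:1 split, value 0.675 - 0.23125g: 0.0675/0.23125 = 29.2%.
- All in Group 1, value 0.675 - 0.175g: 0.0675/0.175 = 38.6%.
- All in Group 4: 0.675 - 0.175g up to g = 1/3, then 0.65 - 0.10g because an ESC start becomes best for X1 = -1. Crossing at 0.0425/0.10 = 42.5%.

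If only one of the two groups is non-empty, the value is 0.6575 at 10%, 0.640 at 20% and 0.6225 at 30%. Early discontinuers are not counted; they would lower these values further.

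**4. Sensitivity to the prognostic terms.** The model also contains 0.25·X2 - 0.25·X3. The prevalences p2 and p3 are not printed individually, only that p_l "ranges from 0.5 to 0.9 and X_l are coded to take values" -1 and 1. The mean of these terms is m = 0.25(2p2 - 1) - 0.25(2p3 - 1) = 0.5(p2 - p3), between -0.2 and 0.2. The printed table takes m = 0. If the value includes m:
- The optimum lies between 0.475 and 0.875.
- The treatment part needed to meet the bar is 0.6075 - 0.1m, between 0.5875 and 0.6275.
- The even-split crossing moves between 30.4% (m = 0.2) and 16.5% (m = -0.2).
- The printed rule without phenotypic markers (0.60) is 0.60/0.675 = 88.9% of the optimum at m = 0. Setting (0.60 + m)/(0.675 + m) = 0.9 gives m = 0.075, so it would meet the 90% bar itself once p2 - p3 exceeds 0.15.

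**5. Monte Carlo standard error.**
- √(0.81 × 0.19/5000) = 0.0055.
- The largest possible value at 5,000 independent replicates is 0.5/√5000 = 0.0071.
- Solving back, 0.81 × 0.19/0.009² = 1,900 replicates, or 1,705 to 2,130 if 0.009 is rounded from 0.0095 to 0.0085.

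**The case against.** The strongest reply is that no error in the 80% has been shown. The printed model is expressly one scenario among several, and Section 10.4.4 refers to group proportions assumed for sizing, so the unprinted runs may well have modelled the classes. The SAP also cites a statistical design paper, not supplied here, that may hold the details. This stands, and it is why the 80% is not called too high or too low. It leaves the only optimum shown in the protocol, which the SAP names as the source, as one that Section 10.4.4 cannot deliver.

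A second reply is that an unrestricted oracle is a legitimate benchmark, since Section 13.1 defines the value without restricting options by class. An unrestricted optimum is at least as high as a restricted one, so scoring restricted regimes against it would be conservative. That is fair, but the protocol does not say this was done. In the cases above where the best deliverable value is below 0.6075, no deliverable regime could succeed at all.

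Third, the class shares here are assumed and overlaid on a model with no response term. That is also fair: the values in steps 3 and 4 show a range and are not estimates. The mismatch with Table 10.1 in step 2 needs no assumed shares.

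Finally, the standard error matters little. The 95% interval for the 81% is 79.2-82.8% with 0.009 and 79.9-82.1% with 0.0055. The replicate count may be the wrong figure instead. Both points are accepted.

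With 805 randomized according to the SAP, against about 740 planned, a re-run cannot change the size or conduct of the trial. It can still change what the 80% is said to mean.

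**Conclusion.** The point holds and should be fixed. The printed optimal rule conflicts with Section 10.4.4 in two ways. Its open Stage 1 entry is wrong under Table 10.1, where the achievable value runs from 0.60 to 0.675 depending on the start. Its pair for every participant is unavailable to Group 1, non-ESC Group 4 and early discontinuers. Under the printed model the best deliverable value is below 0.675 whenever Group 1 or non-ESC Group 4 is non-empty. It falls below the 0.6075 bar only when the two groups together exceed about 23.5% (even split), 29% (3:1) or 39-43% (all in one group). Those thresholds assume shares equal across Stage 1 treatments and X1, and prognostic terms that average zero.

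The text does not show whether the 80% at 630 completers used the same benchmark, so the direction and size of any error in it are unknown. Separately, 81%, 5,000 replicates and 0.009 cannot all be right.

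**What to change.** Keep the sample size, and change the following:

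1. Re-run the simulation, or state that it was already run, with Stage 2 options limited by the response classes and Table 10.1, using the group and augment/switch proportions already assumed.
2. Define the optimum over those options, and replace the open Stage 1 entry in the optimal rule with the starts that reach it.
3. Restate the probability in Sections 4.1, 7.1 and 13.2 as relative to the best regime deliverable under Section 10.4.4, and give that regime's value.
4. Correct either the standard error (0.0055 at 5,000 replicates) or the replicate count (about 1,900 for 0.009).
5. In the restated text, print the assumed group proportions, the Stage 2 allocation, the covariate prevalences, the Lasso penalty rule, and the trial size behind the 81%.

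The cost is a simulation run, or a statement that it was done, and revised wording in three sections. The restated probability may be less favourable, and the benchmark will be below 0.675 if Group 1 or non-ESC Group 4 is non-empty. No extra patients and no change in trial conduct are needed.
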